4.0 Eligibility Criteria

Inclusion:

- between the ages of 18 and 50, must have at least a 6th grade education, ability to speak and read English for all phases.

Exclusion:

- **Medical** - if they are on psychotropic medications for ADHD, other mental illness or medication for cancer, epilepsy (i.e. individuals with any history of seizure disorder), migraines, or other neurological syndromes, or AIDS (which can cause cognitive deficits (Watkins & Treisman, 2015), history of head trauma, history of cognitive impairments, metal implants in the head or under the scalp, personal experiences consistent with symptoms of psychosis (i.e. hearing or seeing things that aren't there, being secretly controlled, or having special powers, seeing or hearing things that aren't really there), history of holes bored into skull or known fissures in cranial bones
- **MRI Safety** - Subjects will be excluded if they do not meet fMRI safety screening criteria (i.e. metal implants in their body, tattoo on head or neck, permanent jewelry, etc.) or if a participant uses an IUD for birth control they will be excluded unless the subject can document the model of the IUD and we can verify its safety for the MRI environment. Pregnancy should be self-reported, and a pregnant test will not be administered. Participants must weigh less than 440 lbs. Presence of pacemakers

5.0 Outcome Characteristics and Endpoint Definitions:

For Study 2.1, Behaviorally, we predict that the Gratton effect on both RT and error rate will be reduced in active TI vs. sham stimulation conditions. We will perform an ANOVA test with factors of on vs. off TI stimulation, previous trial congruent/incongruent, and current trial congruent/incongruent. We expect to find a significant interaction, with post-hoc tests showing reduced effects of previous trial congruency, and reduced interactions of previous trial congruency with current trial congruency. Neurally, we expect to find that the BOLD signal shows a main effect of increase during the TI stimulation vs. sham. Also, we expect to find that the contrast of dACC responses to incongruent minus congruent trials is attenuated in the active TI stimulation condition vs. no-TI. If so, we will conclude that TI disrupts cognitive control by attenuating the monitoring function of dorsal ACC. Potential problems and alternate approaches It is possible that TI stimulation here may enhance rather than disrupt neural function, in which case we may find larger rather than smaller Gratton effects with TI. In that case, we will ask whether the contrast of BOLD activity for incongruent minus congruent trials in dorsal ACC is correspondingly increased during active TI vs. sham stimulation.

For Study 2.2, behaviorally, we predict that TI will disrupt the dACC, leading to a smaller likelihood of skipping difficult trials. We will perform a logistic regression to determine how TI stimulation (on vs. off) and trial difficulty (easy vs. hard), and their interaction, predict the probability of skipping a trial. Neurally, we expect to find increased BOLD signal both for TI stimulation and for skipping a trial, in overlapping regions. Potential problems and alternate approaches As with Study 2.1, it is possible that TI stimulation here may enhance rather than

disrupt neural function, in which case we may find an increase rather than decrease in the probability of skipping with T1 stimulation. We will use two-tailed statistical tests to detect this possibility.

For Study 2.3, we will test whether T1 to dorsal ACC increases or decreases foraging probability, or alternatively, whether T1 reduces the reaction time differences of easy vs difficult decisions.

6.0 Statistical Analysis and Sample Size:

Power Analysis: From the pilot data shown in Fig. 2, we used the effect size of the stim-sham contrast to calculate the number of subjects required to detect a significant cluster of activity in the region shown. We assumed $p<0.001$ as the cluster defining threshold and required 90% power. The required number of subjects is 25, and we budget for 30 subjects per study to allow for attrition. We do not have effect size estimates for the behavioral effects of Aim 2.

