3.0 Design

Overview. This is a study examining the effects of TI on brain activity as measured by fMRI BOLD signals (Aim 1), and the effects of TI-related changes in deeper brain region activity on cognitive functions. Both aims build on our preliminary results showing focal changes in BOLD signals resulting from TI. In Aim 1, we will first establish the effects of TI on BOLD signals, then show that

these are not confounded with the high frequency carrier signal effects alone, and then show how TI can manipulate activity can propagate across brain networks to influence functionally connected brain regions. In Aim 2, we apply TI to stimulate a deeper brain region, the dorsal anterior cingulate cortex, to resolve longstanding questions about its causal role in cognition. We anticipate recruiting 200 subjects, allowing for attrition to achieve our goal of 30 subjects for each individual study below.

Subjects will spend 2-3 hours for the session and be paid \$35/hour.

Aim 1: Test and characterize the effects of TI on the fMRI BOLD signal

In all studies, we will administer the Stimulation experience scale before starting the stimulation and after the stimulation session is complete. Subjects will also be asked periodically to rate any discomfort on a scale of 1-5 (5=highest discomfort), and indicate the location and qualities of any discomfort.

Study 1.1. Test the effect of TI in NAcc, controlling for the effects of high frequency

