Study 2.1. Test whether 20Hz TI in the dACC enhances or disrupts cognitive control. For this, n=30 human subjects will be placed in the fMRI scanner to perform a flanker task(Eriksen & Eriksen, 1974), in which subjects must indicate whether the central arrow points left or right. The

trials will be 50% congruent (“<<<<” and “>>>>”) and 50% incongruent (“<<><<” and “>><>>”) trials. Previous work shows not only elevated reaction time and error rates for incongruent trials, but also a “Gratton effect” in which RT and error rate (as well as dACC activity) are even more elevated for incongruent trials that follow a previous congruent trial (Botvinick et al., 1999). This is arguably because cognitive control-related activity in the dACC prior to the start of the trial was lower, thus requiring more cognitive control-related activation as a reaction to the incongruent task stimulus(Botvinick et al., 1999). We will test whether the Gratton effect is reduced by TI to the dACC in the scanner, and whether this is accompanied by increased baseline dACC activity due to TI. Subjects will be divided into two groups. One will receive 2 consecutive eight-minute blocks of TI stimulation (2000 and 2020 Hz in the two electrode pairs, or alternatively the most effective beat frequency identified in Aim 1) to dorsal ACC, followed by 2 eight-minute blocks with no-TI stimulation, as subjects perform the flanker task in the fMRI scanner. The second group of subjects will undergo an identical procedure, except that the first two blocks will be no-TI stimulation, followed by 2 eight-minute blocks of TI stimulation. In all subjects, blocks 1 and 3 will include the Flanker task, and blocks 2 and 4 will include the visual search task of Magno et al., (2006). The visual search task will provide the data needed for Study 2.2.

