Study 2.2. Test the causal role of dorsal anterior cingulate in avoidance. We will apply TI stimulation as in Study 2.1 to the dorsal ACC with subjects in the fMRI scanner, and for efficiency, we will run this task on the same subjects as Study 2.1 concurrently and without leaving the scanner. Subjects will perform the task of Magno et al. (2006), during blocks 2 and 4 of the sessions described in Study 2.1. Specifically, subjects will perform a visual search task, identifying “target present” or “target absent” within a short deadline. There are two trial types, easy (few non-targets) and hard (many non-targets). They gain +1 reward for correct responses (converted to cash after the session), -1 reward for errors, and they can also skip the trial for 0 reward to avoid risk. Previous work shows dorsal ACC activity only when subjects skip the trial to avoid the risk of an error, but anterior insula activity occurs instead when subjects choose to respond and then make an error (Magno et al., 2006).

Study 2.3. Test the causal role of the dorsal ACC in foraging decisions. Using the TI stimulation of Study 2.1 with humans subjects in the scanner (n=30), subjects will perform a foraging and difficulty task(Shenhav et al., 2014) to adjudicate between competing theories of dorsal ACC, whether it drives foraging or reflects task difficulty. Subjects will be divided into two groups as in Study 2.1 and will perform the task of Shenhav et al. (2014)(Shenhav et al., 2014) during 4 eight-minute blocks, with TI and no-TI conditions in the scanner as in Study 2.1 for each of the two groups. In the task, subjects must decide whether to accept playing a gamble with known probabilities or forage to find a better gamble with more favorable probabilities. The relative value of foraging (RVF), i.e. the difference in expected value for playing the gamble vs. foraging, varies between an easy decision (large positive or negative RVF) or a difficult decision (near-zero RVF).

Risks of participation and mitigation of risks:

Subjects may feel uncomfortable completing the interview. For instance, there are questions about whether they may be pregnant, surgical history, and about the existence of tattoos and piercings on the body. They may decline to answer specific questions or decline to continue participating.

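### Study 2.2's logistic regression of skipping names no subject-level error and no period or order term, so its stimulation test can be conservative or inflated

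*Combined protocol and SAP*

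**What the plan says.** Section 5.0 (Study 2.2) gives one behavioural analysis: "We will perform a logistic regression to determine how TI stimulation (on vs. off) and trial difficulty (easy vs. hard), and their interaction" as predictors of the chance that a trial is skipped. The prediction it serves is that TI disrupts the dACC, "leading to a smaller likelihood of skipping difficult trials". Because TI might instead raise skipping, the plan adds: "We will use two-tailed statistical tests to detect this possibility". It gives no alpha for this test.

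The design is in section 3.0. The search task is done "during blocks 2 and 4 of the sessions described in Study 2.1". One group has TI in blocks 1 and 2 and no TI in blocks 3 and 4. The other follows the same procedure, "except that the first two blocks will be no-TI stimulation, followed by 2 eight-minute blocks of TI stimulation". The Overview describes recruitment as "allowing for attrition to achieve our goal of 30 subjects for each individual study below", and the Study procedure summary assigns order by an alternating list.

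Section 6.0 contains only the imaging power paragraph, with a p-value used "as the cluster defining threshold and required 90% power". On behaviour it says: "We do not have effect size estimates for the behavioral effects of Aim 2". No section names a random subject effect, clustered standard error, per-subject summary, period term or order term for the skip analysis.

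**The concern.** This is a two-period crossover with many binary trials inside each period. Subjects will differ in how readily they skip, and each subject's readiness may also drift between block 2 and block 4. As there is only one block per condition, that drift is inseparable from the subject's response to TI. The appropriate yardstick for the average TI effect is therefore how much the TI minus no-TI shift varies from subject to subject. A regression with only the three listed terms treats every trial as independent and uses a different yardstick.

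This is the only stated behavioural test of the Study 2.2 prediction, and Aim 2 is meant to support causal statements about the dACC. If the shift varies moderately between subjects, a false finding that stimulation changes avoidance becomes more likely. If it does not vary, the test gives up some sensitivity. A reader of the plan cannot tell which applies.

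**Working it through.** **1. Structure (from section 3.0).**

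| Order group | Search block 2 | Search block 4 |
|---|---|---|
| TI first | TI | no TI |
| No TI first | no TI | TI |

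Each subject gives one block per condition, and within a group stimulation coincides with period.

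**2. The plan's own figure.** The 25 subjects required (30 budgeted) come from the imaging contrast. The pilot effect size is not given, so 25 cannot be reproduced, and it does not bear on skipping.

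**3. Inputs.** From the documents: 30 subjects, two orders, two-tailed testing. Assumed: 5% level; 96 trials per block, half of them hard (m = 48); skip log-odds −2.0 (easy) and −0.5 (hard); between-subject intercept SD 1 logit; TI minus no-TI shift with mean 0 and SD τ.

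**4. Closed-form check, hard trials.** The listed model is saturated, so its hard-trial TI effect is the log odds ratio of the pooled 2×2 table. Let p be a subject's hard-trial skip probability, P its mean and w = p(1−p). With n subjects:

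- variance the model reports ≈ 2 / [n m P(1−P)]
- actual variance ≈ [2E(w)/m + τ²E(w²)] / [n {P(1−P)}²]
- ratio R = [2E(w) + mτ²E(w²)] / [2P(1−P)]

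Integrating over a normal intercept (mean −0.5, SD 1) gives P = 0.398, P(1−P) = 0.2396, E(w) = 0.1990 and E(w²) = 0.04227. So R = (0.3980 + 2.029τ²) / 0.4792, and the false-positive rate is 2[1 − Φ(1.96/√R)].

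| τ (logits) | R | Closed form | Simulated (20,000 runs) |
|---|---|---|---|
| 0 | 0.83 | 3.1% | 3.2% |
| 0.1 | 0.87 | 3.6% | 3.6% |
| 0.2 | 1.00 | 5.0% | 5.0% |
| 0.3 | 1.21 | 7.5% | 7.5% |
| 0.5 | 1.89 | 15.4% | 15% |
| 0.8 | 3.54 | 29.8% | 28% |

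R does not contain n, so recruiting more subjects does not cure the problem. R rises with m, so longer blocks worsen it.

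**5. Where the error changes sign.** Since P(1−P) − E(w) = Var(p), R = 1 at τ² = 2Var(p) / [mE(w²)]. With Var(p) = 0.0406, τ² = 0.0812/2.029 = 0.040, so τ = 0.20. For intercept SD 0.5: 2 × 0.01262 / (48 × 0.05092) = 0.0103, τ = 0.10. For SD 1.5: 2 × 0.07018 / (48 × 0.03437) = 0.085, τ = 0.29. Simulation gave about 0.1, 0.2 and 0.3. The test averaged over difficulty crosses 5% nearer 0.15 in the base case.

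**6. Other settings (simulated).**

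- Hard trials at τ = 0.3, 0.5, 0.8: 6%, 11%, 20% with 60 trials per block; 11%, 22%, 39% with 160.
- Averaged over difficulty at τ = 0, 0.3, 0.5, 0.8: 3.5%, 11%, 22%, 38%.
- TI × difficulty: 3.5–5.6% in the base case and 2–7% over all settings, when the interaction does not vary between subjects. It reaches about 9% and 16–17% if the interaction varies with SD 0.5 and 0.8.

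**7. Alternatives, hard trials, at τ = 0, 0.3, 0.5, 0.8.**

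- Random intercept only: 6%, 11%, 22%, 37%.
- Random intercept, stimulation slope and difficulty slope, fixed period: 4.8%, 5.9%, 6.5%, 7.0% against chi-square; 3.2%, 4.6%, 5.0%, 5.8% against F(1,28). These rest on 800 runs per setting (Monte Carlo standard error about 0.8 point).
- Per-subject log-odds difference with order group (30 − 2 = 28 df): 4.5–5.3% in every setting.

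**8. Period.** With orders 15/15, a true effect of 0.35 logits and τ = 0.5, omitting order lowers hard-trial power from 75% to 70% or 58% for a period effect of 0.25 or 0.5 logits; with order it stays at 74–75%. Unequal orders bring bias. In a separate null simulation (40 trials per cell, skip rates 10% and 40%, period shift 0.5 logits, τ = 0), the listed model rejected 3.5–6.1% at 15:15, 6.5–10.1% at 14:11 and 36–48% at 17:8, the ranges spanning the hard-trial and averaged tests. A per-subject contrast with order group stayed at 4.5–4.8%.

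**The case against.** The strongest reply is that the plan is silent rather than wrong. One sentence listing the effects of interest does not fix the error structure, and the investigators may intend a mixed model. It stands that nothing excludes one. But the only model on paper gives a wrong standard error in one direction or the other, and the natural default of a random intercept alone does not repair it (11% at τ = 0.3). The slope has to be written down.

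Second, every rate rests on assumed trial counts, skip rates and variances. At τ up to 0.3 the base-case hard-trial rate is only 3–8%, and the figures near 30–40% need τ = 0.8. This stands: the calculations show the mechanism and its range, not the rate this study will have.

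Third, the plan does not designate the hard-trial effect as decisive, and the prediction could be read through the interaction, which is largely unaffected unless it too varies between subjects. That is fair. However, the effect averaged over difficulty is inflated more than the hard-trial effect, and the plan should say which test carries the claim.

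Fourth, alternating assignment makes the orders nearly equal, so the period term is secondary. This is right at 15/15. It matters more if attrition unbalances the orders, although 17:8 is an extreme split with no support in the documents.

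**Conclusion.** The concern holds. Each subject contributes one TI and one no-TI search block, and the listed regression has no term that makes subjects the unit of error. That conclusion follows from the design and needs no assumed value. The direction and size of the resulting error do depend on unstated quantities. Over the settings tried, the hard-trial test at an assumed two-sided 5% level ranged from about 2% (large baseline differences, no variation in the shift) to 39% (160 trials per block, shift SD 0.8). The change from conservative to inflated comes at a shift SD of 0.1–0.3 logits, depending on baseline spread. The missing subject-level term is the main fault. The missing period term costs power when orders are equal and introduces bias only when they are not. It should be corrected before the data are analysed.

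**What to change.** Specify a mixed-effects logistic regression with a subject random intercept, a random stimulation slope that is kept in the model, a random difficulty slope, a random interaction slope if estimable, and a fixed period effect. Name the contrast that tests the prediction (the hard-trial TI effect fits it best), state its alpha, and refer it to subject-based degrees of freedom: 28 with 30 subjects and two orders.

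State the fallback for non-convergence in advance. For each subject, compute the TI minus no-TI difference in empirical log-odds of skipping (0.5 added to each cell), separately for hard and easy trials. Analyse the hard-trial difference, and the hard minus easy difference for the interaction, with order group as a factor. Making this the primary analysis would also be sound, given how steadily it held its level; the choice must be fixed beforehand.

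The cost is wording, a few lines of code and one degree of freedom for period. P-values for skipping may become less favourable. If the shift does not vary between subjects, the per-subject analysis has slightly less hard-trial power than the listed model: 77% against 80% at a 0.25-logit effect, and 58% against 60% at 0.2.
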